**Diagnosis and key inclusion criteria:**

Subjects complying with all of the following criteria will be included into the clinical study:

1. Written informed consent received from the subject.
2. Men and women aged 18 to 45 years old, inclusive.
3. Newly diagnosed active pulmonary tuberculosis confirmed by characteristic radiological findings (infiltration, dissemination, and destruction) in chest X-ray or computed tomography not involving other

**Name of active substance:**PBTZ169 Hydrochloride

---

organs or involving one or more of the following: the larynx, the trachea, the bronchi, and lymph nodes.

4. The patient's sputum volume must be enough for any tests provided for under the Protocol but not less than 4 to 5 mL at screening.
5. Acid-fast mycobacteria found in sputum smear microscopy (1+ and more using the luminescent dye microscopy according to Order of the Russian Ministry of Health No. 109 dated March 21, 2003, latest revision) and tuberculosis mycobacterial DNA found in molecular genetic tests.
6. A body weight of at least 51 kg.
7. Body mass index of 18.5–25 kg/m^2.
8. The ability (according to the investigator's opinion) to comply with all requirements of the Protocol.
9. Agreement to use reliable contraception methods during the study and 3 months after the last dose of the drug, including temporary abstinence from sex or double contraception combining male condoms with at least one of the following:
  - Using hormonal contraception
  - Using aerosols, creams, suppositories, and other agents containing spermicides
  - Using an intrauterine device

Subjects who meet any of the following criteria will not be included in the clinical study:

1. Extrapulmonary localization of tuberculosis.
2. Resistance to rifampicin and/or isoniazid found in molecular -genetic tests on sputum samples.
3. Administration of any antituberculosis drugs from the moment of tuberculosis diagnosis to enrolment in the study.
4. Absolute indications for surgical treatment of tuberculosis at screening.
5. Testing positive for syphilis or HIV infection serological markers at screening, active hepatitis, or decompensated liver cirrhosis.
6. History of allergic reactions.
7. Laboratory renal and/or hepatic parameters measured as follows (with due regard to the laboratory's reference range):
  - AST > 2.0 x upper limit of normal values (ULN)

**Name of active substance:**PBTZ169 Hydrochloride

---

---

- ALT > 2.0 x ULN
  - Total bilirubin > 1.5 x ULN
  - Creatinine > 1.5 x ULN
8. Individual intolerance to any ingredients of the study drug.
  9. History of malignant tumors, except for basal cell carcinoma.
  10. Decompensated severe chronic somatic diseases, including cardiovascular, bronchopulmonary, neuroendocrine, ENT, -gastrointestinal, hepatic, renal, blood, skin diseases, and other somatic or mental diseases that the investigator believes to prevent the subject's enrolment.
  11. Gastrointestinal- surgery (except for appendectomy performed more than 1 year before the screening).
  12. Any mental disorders that can affect the patient's compliance with the Protocol.
  13. Diabetes mellitus.
  14. Acute viral and bacterial infections at enrolment or within 2 weeks prior to enrolment.
  15. Alcoholism (unless the investigator believes the subject to be able to abstain from alcohol consumption during the study) or substance abuse.
  16. A positive test for narcotic and psychotropic products.
  17. Regular administration (including topical) of any hormonal drugs for over 1 week within 30 days before the screening (except for oral hormonal contraceptives and hormonal intrauterine devices).
  18. Use of cytotoxic drugs within 30 days before the screening.
  19. Repeated administration of any drugs where the instruction for medical use mentions nervous system, hemodynamics, and liver function adverse events as "very frequent" ( $\geq 10\%$ ) or "frequent" ( $\geq 1\%$  and  $< 10\%$ ) within 21 days before the screening.
  20. Pregnancy or lactation.
  21. Planned conception or sperm donation during the study after the study drug administration or within 3 months after the date of the last drug administration.
  22. Participation in other clinical trials of drugs within less than 3 months before the screening.

**Name of active substance:**

PBTZ169 Hydrochloride

---

**Study drug, dose, administration, and batch number:**

Study drug code: PBTZ169

Brand name: none

International nonproprietary name: none

Dosage form: 80 mg capsules.

Pharmacotherapeutic group: antituberculosis drug

ATC code: J04A

Dose and administration route: patients receive PBTZ169 orally once a day in the morning in the fasting state in the following doses:

- Group 1: 160 mg daily
- Group 2: 320 mg daily
- Group 3: 640 mg daily

**Name of active substance:**PBTZ169 Hydrochloride

---

---

**Duration of treatment with the study drug:**

Monotherapy for 14 consecutive days.

**Comparator, dose and administration, batch number:**

Brand name: Isoniazid

International nonproprietary name: isoniazid

Dosage form: 300 mg tablets.

Pharmacotherapeutic group: antituberculosis drug

ATC code: J04AC01

Dose and administration route: Isoniazid is prescribed to subjects randomized into Group 4 in the daily dose of 600 mg of orally in the morning after meals.

**Comparator treatment duration:**

Monotherapy for 14 consecutive days. Isoniazid is then continued as part of the combined antituberculosis therapy.

**Assessment parameters:****Efficacy:*****Primary efficacy endpoint:***

- Early bactericidal activity 14 days from the monotherapy start date (EBA0-14).

***Variables for the secondary efficacy endpoint:***

- Early bactericidal activity 2 days from the monotherapy start date (EBA0-2).
- Early bactericidal activity 7 days from the monotherapy start date (EBA0-7).

**Safety:*****Variables for the safety endpoint***

- Adverse events
- Changes in vital signs
- Results of laboratory tests (complete blood count, biochemical blood analysis, urinalysis)
- ECG findings
- Physical examination results

**Name of active substance:**

PBTZ169 Hydrochloride

**Pharmacokinetics:*****Variables for pharmacokinetics evaluation:***

- Maximum concentration ( $C_{\max}$ ) within the dosing interval of 24 hours after single and multiple dosing
- Minimum concentration ( $C_{\min}$ ) within the dosing interval after single and multiple dosing
- Trough concentration ( $C_{\text{trough}}$ ) (measured 24 hours after the first dose administration, prior to the last dose, and 24 hours after the last dose)
- Time to maximum concentration ( $T_{\max}$ ) within the dosing interval after single and multiple dosing
- Area under the concentration–time curve within the dosing interval ( $AUC_{0-24}$ ) after single and multiple dosing
- Area under the concentration–time curve within the interval from 0 to the last measurement value above LLoQ ( $AUC_{0-t}$ ) after single and multiple dosing
- Area under the concentration–time curve within the interval from 0 to infinity ( $AUC_{0-\infty}$ ) after single and multiple dosing
- Mean concentration ( $C_{\text{ss,av}}$ ) within the dosing interval after multiple dosing
- Fluctuations (%) within the dosing interval after multiple dosing ( $[(C_{\max}-C_{\min})\times 100\%/C_{\text{ss,av}}]$ )
- Apparent total clearance following oral administration ( $Cl_t/F$ ) as measured after single and multiple dosing
- Distribution volume ( $V_d$ ) measured after single and multiple dosing
- Half-life ( $T_{1/2}$ ) measured after single and multiple dosing
- Elimination constant  $k_{el}$  measured after single and multiple dosing.

**Pharmacodynamics:**

- $C_{\max,ss}$  and  $AUC_{0-24,ss}$  measured after multiple dosing after 14 days of therapy are used for early bacterial activity  $EBA_{0-14}$  and  $EBA_{2-14}$  as parameters for PK comparison.

$C_{\max}$ ,  $C_{\min}$ , and  $AUC_{0-24}$  measured after the first dose administration are used for early bacterial activity  $EBA_{0-2}$  as parameters for PK comparison.

**Name of active substance:**PBTZ169 Hydrochloride

---

**Statistical methods:**

Descriptive statistics will be provided for all demographics and other baseline characteristics, efficacy and safety parameters, and changes in them (if applicable) in the course of the study by means of assessment time points and treatment groups. Descriptive statistics for quantitative variables include mean value, standard deviation (SD), minimum and maximum values, and the number of valid observations. Qualitative data is presented as rates and percentages. 95% confidence intervals around point estimations are provided as well (where applicable).

***Efficacy analysis***

According to the EMA Guidance, early bactericidal activity (EBA) assessment should be based on determining the count of live mycobacteria in the patient's sputum during monotherapy with the drug. The primary method of determining mycobacterial count used is inoculating agar with sputum to count CFU/mL. The method is chosen as it is used as the primary method in nearly all studies assessing early bactericidal activity, which means it can be considered conventional [16–19].

The method of quantitative PCR for counting mycobacterial cells in sputum is used as a secondary method for secondary analysis [23].

All assessments of  $\log_{10}$  CFU/mL sputum, mycobacterial cell count estimates obtained with PCR, and their changes from baseline are tabulated by measurement points and treatment groups.

In the primary analysis of treatment efficacy, changes from baseline in  $\log_{10}$  CFU/mL sputum (for agar inoculation) 14 days after the therapy start date are estimated. Changes in  $\log_{10}$  CFU/mL sputum 2 and 7 days after the therapy start date are also estimated in the secondary analysis of treatment efficacy. Early bactericidal activity (EBA) is assessed as a change in  $\log_{10}$  of CFU/mL of sputum specified for the treatment day [24] with a two-sided 95% confidence interval.

Though sample size is estimated empirically disregarding formal comparisons between the two dose levels, the Kruskal–Wallis test is used to compare the values for different dose levels of the study drug at a two-sided 5% significance level.

The history of mean changes in  $\log_{10}$  CFU/mL from baseline by assessment points is presented graphically by treatment groups.

The Jonckheere–Terpstra test is used to identify the trend for the primary efficacy endpoint depending on the increase in dose level (increasing  $EBA_{0-14}$  for increasing doses).

A similar efficacy analysis (based on changes in  $\log_{10}$  cells/mL) is carried out by determining mycobacterial cell count with quantitative PCR.

Graphical methods and calculation of correlation coefficients between individual measurements obtained using the two quantification methods are used to analyze the

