**Name of active substance:**

PBTZ169 Hydrochloride

---

State Budgetary Health-Care Institution of the Arkhangelsk Region Arkhangelsk Clinical Tuberculous Dispensary Address: [name] Principal investigator: [name]

Study Center 9:

Regional State Budgetary Health-Care Institution Tomsk Phthisiatric and Pulmonologic Medical Center Address: [name] Principal investigator: [name]

Study Center 10:

State Health-Care Institution of the Samara Region Tolyatti Municipal Tuberculous Dispensary Address: [name] Principal investigator: [name]

Study Center 11:

Federal State Budgetary Institution Novosibirsk Tuberculosis Research Institute of the Ministry of Health Care of the Russian Federation Address: [name] Principal investigator: [name]

Study Center 12:

State Autonomous Health-Care Institution Republican Clinical Tuberculosis Dispensary Address: [name] Principal investigator: [name]

Study Center 13:

Federal State Budgetary Institution Saint Petersburg Research Institute of Phthisiopulmonology of the Ministry of Health Care of the Russian Federation Address: [name] Principal investigator: [name]

**Publications (references):** none**Phase of drug development:** IIa

**Goals:** to study the efficacy of PBTZ169 in the daily doses of 160, 320, and 640 mg based on its early bactericidal activity, safety, and pharmacokinetics of PBTZ169 p.o. as monotherapy for 14 days in patients with newly diagnosed microbiologically proven respiratory tuberculosis with preserved susceptibility to Isoniazid and Rifampicin.

**Design:** this study is a randomized open-label study of efficacy (in terms of early bactericidal activity), safety, and pharmacokinetics of PBTZ169 in parallel groups with active control in patients with newly diagnosed respiratory tuberculosis. The study comprises the following stages:

**Name of active substance:**PBTZ169 Hydrochloride

---

---

- Screening, up to 10 days
- Monotherapy, 14 days
- Follow-up, 7 days

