Screening procedures are carried out within 10 days before randomization. Screening procedures can be carried out on an outpatient or inpatient basis. If the screening procedures are performed outpatiently, subjects are admitted to hospital on the day before the first dose of the study drugs. If the screening procedures are performed inpatiently, subjects stay hospitalized for the purpose of participation in the clinical study.

Eligible subjects are randomized. During randomization, each subject is assigned a randomization number generated by the IWRS. Each patient is assigned to one of the following four groups based on the randomization number:

- Group 1: subjects receive PBTZ169 capsules at a daily dose of 160 mg for 14 days as a monotherapy, after which the drug is discontinued, and standard antituberculosis therapy is prescribed (hereinafter, standard antituberculosis therapy is defined as the tuberculosis therapy provided for under Order of the Ministry of Health of the Russian Federation No. 951 dated December 29, 2014). Up to 15 subjects are planned to be randomized to this group.
- Group 2: subjects receive PBTZ169 capsules at a daily dose of 320 mg for 14 days as a monotherapy, after which the drug is discontinued, and standard antituberculosis therapy is prescribed. Up to 15 subjects are planned to be randomized to this group.
- Group 3: subjects receive PBTZ169 capsules at a daily dose of 640 mg for 14 days as a monotherapy, after which the drug is discontinued, and standard antituberculosis therapy is prescribed. Up to 15 subjects are planned to be randomized to this group.
- Group 4: subjects receive isoniazid tablets at a standard daily dose of 600 mg for 4 days as a monotherapy, after which standard antituberculosis therapy follows. Up to 7 subjects are planned to be randomized to this group.

All study procedures are conducted in the subjects and documented under the randomization number.

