**Name of active substance:**

PBTZ169 Hydrochloride

---

Nocturnal sputum is collected from all subjects in the morning at V1. After that, every patient received the study drug (PBTZ169 or isoniazid) as a monotherapy for 14 consecutive days. After 14 days of monotherapy (Day 15 of the study, V8), PBTZ169 is discontinued in Groups 1 to 3 (Day 14 being the day of the last PBTZ169 dose). Standard therapy is initiated 3 days after the monotherapy end date (Day 18 of the study, V10). Standard therapy drugs are resumed in Group 4 (standard dose of isoniazid) without a break—that is, the day following the monotherapy end date (Day 15 of the study). Patient monitoring during clinical study is continued on a hospital basis and ended 7 days following the monotherapy end date.

Venous blood samples are taken from all subjects in Groups 1, 2, and 3 (PBTZ169 monotherapy) to measure PBTZ169 levels. Blood samples are drawn before the first dose of PBTZ169 (0 min time point) and later at the following time points after the first dose: in 0:20, 0:40, 1:00, 1:30, 2:00, 2:30, 3:00, 4:00, 6:00, 8:00, 10:00, 12:00, and 24:00 (hr:min). Blood samples are also taken before the last dose of PBTZ169 (0 min time point) and later at the following time points after the last dose: after 0:20, 0:40, 1:00, 1:30, 2:00, 2:30, 3:00, 4:00, 6:00, 8:00, 10:00, 12:00, 24:00, 48:00, and 72:00 (hr:min).

All venous blood samples are kept in case any additional parameters have to be measured.

Subjects are hospitalized throughout the monotherapy and follow-up periods.

**Number of subjects:** It's planned to randomize 52 eligible subjects for the study, namely 15 subjects in each PBTZ169 group and 7 subjects in the isoniazid group.

The data of subjects who will receive at least one dose of the study drug and whose study drug concentrations are known will be processed in the final statistical analysis of efficacy and pharmacokinetics.

The data of subjects of ITT population will be processed in the final statistical analysis of safety.

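### The isoniazid arm has no pre-specified comparative role: no dose-minus-isoniazid estimate is planned, and the efficacy-set definition, read literally, leaves the arm out

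*Combined protocol and SAP*

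**What the plan says.** All references are to the synopsis in the combined protocol and SAP.

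- **Design.** The trial is randomised and open-label, "in parallel groups with active control in patients with newly diagnosed respiratory tuberculosis".
- **Goals.** The aim is "to study the efficacy of PBTZ169 in the daily doses of 160, 320, and 640 mg based on its early bactericidal activity", together with safety and pharmacokinetics. No comparison with isoniazid is named.
- **Number of subjects.** The planned total is 52, split as "15 subjects in each PBTZ169 group and 7 subjects in the isoniazid group". The same section restricts the final efficacy and pharmacokinetic analysis to dosed subjects with a known study-drug concentration. The Design text schedules blood sampling for PBTZ169 levels in Groups 1, 2 and 3 only.
- **Efficacy analysis.** The sample size is described as empirical. Kruskal–Wallis is used "to compare the values for different dose levels of the study drug" at a two-sided 5% level, and Jonckheere–Terpstra is used for a dose trend in EBA0-14. Counts and changes from baseline are tabulated by treatment group, mean changes are plotted by treatment group, and EBA is given with a two-sided 95% CI.
- **Isoniazid duration.** For Group 4 the Design section says "subjects receive isoniazid tablets at a standard daily dose of 600 mg for 4 days as a monotherapy". Comparator treatment duration says "Monotherapy for 14 consecutive days", and a later paragraph of the Design section also has 14 days for every patient.
- **Status.** The section on pharmacokinetic and pharmacodynamic analysis ends by saying that the planned interim analysis is not done because the study was terminated early.

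**The concern.** Randomising a concurrent control makes an unbiased contrast available: each PBTZ169 dose against isoniazid, in the same laboratories and over the same period. The plan neither estimates that contrast nor says what the control is for. Readers will then put the separate group intervals side by side and judge by eye whether they overlap, which is stricter than looking at an interval for the difference and can hide a real shortfall or surplus.

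The efficacy-set wording raises a second problem. If it is applied as written, Group 4 has no qualifying concentrations and drops out of the efficacy analysis. The by-group tables would then have no isoniazid column, which contradicts the by-group presentation that the same synopsis promises.

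**Working it through.** **1. Plan's own figure.** 3 × 15 + 7 = 52, which matches the stated total. No power, effect size or SD is given, so there is no power figure to reproduce.

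**2. Do the planned tests involve isoniazid?** The study-drug section gives the code PBTZ169, and isoniazid has its own comparator section. The Design text does once use the term study drug for both products. But isoniazid is given at a single daily dose, so it cannot form several dose levels, and a dose trend cannot place it. Even if Kruskal–Wallis did take in Group 4, it is an omnibus test and yields no estimate for any dose against isoniazid.

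**3. Does the efficacy set include Group 4?** The condition is a known study-drug concentration. If that means PBTZ169, Group 4 has none. If it means either product, isoniazid levels would be needed, and no sampling for them is scheduled in the text. Both literal readings exclude Group 4.

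**4. Precision at the planned sizes**, in units of a common SD of EBA:

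- One PBTZ169 arm: t(0.975, 14)/√15 = 2.145/3.873 = 0.554 SD.
- Isoniazid arm: t(0.975, 6)/√7 = 2.447/2.646 = 0.925 SD.
- Difference, 15 v 7: t(0.975, 20) × √(1/15 + 1/7) = 2.086 × 0.4577 = 0.955 SD.

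**5. Cost of reading by eye.** Two separate intervals stop overlapping only when the means differ by 0.554 + 0.925 = 1.479 SD. The interval for the difference excludes zero from 0.955 SD. The ratio is 1.479/0.955 = 1.55, so judging by overlap asks for a gap about 55% larger. This takes both sample SDs equal to the common SD.

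**6. On the log10 CFU/mL scale.** The documents give no SD, so these values are assumptions:

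| Assumed SD | Half-width of difference, 15 v 7 |
|---|---|
| 0.5 | 0.48 |
| 1.0 | 0.95 |
| 1.5 | 1.43 |

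**7. Which time points can be compared now?** Both isoniazid texts have the control on monotherapy at day 2. At days 7 and 14 they disagree: under the 4-day text Group 4 would already be on standard combination therapy, so its EBA0-7 and EBA0-14 would not be monotherapy values.

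**The case against.** The best defence is that the control is meant to be descriptive. The stated goal concerns PBTZ169 alone, the sample size is empirical, and 7 subjects are too few for a sensitive comparison. With 15 v 7, 80% power at two-sided 5% needs a difference of about 1.35 SD (t-based, unadjusted), and power at 1 SD is about 55%. This stands as an argument against a formal test. It does not argue against an interval: the plan already runs a 5% test between doses on the same empirical sample size, and a descriptive estimate claims less than that. Nor do the documents state the descriptive role, so a reader has to infer it.

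Two stronger readings are tempting, and the documents support neither.

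- A reader might infer that the control contributes nothing to the efficacy conclusion. The by-group tables, curves and EBA intervals on their face include isoniazid, so it has a descriptive place unless the efficacy-set wording removes it.
- A reader might infer that, without the contrast, a weak drug cannot be told from a failing assay. It is isoniazid's own EBA, already planned by group, that checks the assay. A difference would not: if the assay failed, both arms would read low and the difference would be near zero, just as for two equally active drugs.

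It is also fair to object that a change made now comes after early termination of an open-label trial, and that the remaining numbers may leave the contrast with little information. Both points stand and belong in the labelling.

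**Conclusion.** The concern holds in a limited form. In the synopsis-level text available, isoniazid has no pre-specified comparative role: the between-group tests concern PBTZ169 dose levels, and no difference, interval or margin against the control is planned. Separately, the efficacy-set definition read literally excludes Group 4 and conflicts with the by-group presentation.

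No planned analysis is invalidated. What is lost is a direct interval on the only randomised contrast with the control, with a half-width of about 0.95 SD at the planned 15 v 7. That figure assumes a common SD, approximate normality and all randomised subjects evaluable. Final arm sizes are not in the documents, so the loss of precision after early termination cannot be quantified here; any smaller arms give a wider interval. A fuller section elsewhere that assigns the control a role or defines another efficacy set would change the conclusion.

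**What to change.** 1. Define the efficacy set without conditioning on drug concentrations, so that Group 4 is included. Keep the concentration condition for the pharmacokinetic set.
2. State what the isoniazid arm is for. Add one table giving, for each PBTZ169 dose, the difference from isoniazid in EBA with a two-sided 95% CI and no hypothesis test.
3. Report EBA0-2 first. Report EBA0-7 and EBA0-14 once the 4-day and 14-day isoniazid monotherapy passages are reconciled with each other.
4. Label the contrast descriptive, and also post hoc if it is added after any data were seen. Show the actual number in each arm beside every interval.

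The cost is a few lines of SAP text and one table. The downside is wide intervals, which a hurried reader could take as evidence of similarity; the descriptive label and the arm sizes should guard against that.

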**Name of active substance:**

PBTZ169 Hydrochloride

---

consistency of the results between the two methods of determining mycobacterial count.

Only available measurements are used in efficacy analysis. No missing values are restored. The analysis is based on average values for each measurement point. An additional analysis at the maximum of two measurements is carried out (with the highest number of CFU or MBT DNA copies using agar inoculation and quantitative PCR, respectively).

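### Correlation is the only numerical measure named for CFU–PCR consistency; a paired difference in fall with a 95% CI would be a cheap, low-priority addition

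*Combined protocol and SAP*

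**What the plan says.** All of this is in the synopsis, under Statistical methods and its Efficacy analysis subsection.

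- **Aim and tools.** The plan names "Graphical methods and calculation of correlation coefficients between individual measurements obtained using the two quantification methods" in order to examine the "consistency of the results between the two methods of determining mycobacterial count". It does not state the type of plot, the type of coefficient, or whether coefficients are by day or pooled over days.
- **Status of PCR.** "The method of quantitative PCR for counting mycobacterial cells in sputum is used as a secondary method for secondary analysis". CFU on agar is the primary method, and EBA is defined as a change in log10 CFU/mL.
- **Other planned output on both methods.** Log10 CFU, PCR counts "and their changes from baseline are tabulated by measurement points and treatment groups". A parallel efficacy analysis "is carried out by determining mycobacterial cell count with quantitative PCR". The general paragraph on statistical methods adds SDs, numbers of valid observations and, where applicable, 95% confidence intervals.
- **Data used.** "Only available measurements are used in efficacy analysis. No missing values are restored". "The analysis is based on average values for each measurement point", with an additional analysis on the larger of two measurements, that is, the one "with the highest number of CFU or MBT DNA copies using agar inoculation and quantitative PCR, respectively".

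The text names no paired CFU–PCR difference, limits of agreement, concordance coefficient or regression of one method on the other.

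**The concern.** The stated aim is consistency between two ways of counting mycobacteria. Because EBA is a change in log10 count, the natural question is how far the fall measured by PCR differs from the fall measured by CFU in the same patient. A correlation coefficient cannot answer it. It is unchanged by linear rescaling, so it can stay high when PCR registers only part of the fall. Coefficients pooled over days also mix between-patient spread with the common fall over time.

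The two methods count different things, DNA copies and live organisms, so equal falls need not be expected. The size of the gap is then the useful descriptive result, and it is the one quantity the consistency analysis does not name. At stake is only how the PCR results are read beside the CFU results.

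**Working it through.** **Inputs from the documents.** Planned group sizes are 15, 15, 15 and 7 (3 × 15 + 7 = 52), and efficacy analysis uses available measurements only. The documents give no SDs, expected fall, missingness rate, final number of pairs or agreement figure, so there is no stated figure to reproduce.

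**Assumed inputs (illustration only).** Days 0, 2, 7 and 14; mean CFU fall 1.4 log10 by Day 14, linear and equal at all doses; SD of fall 0.4 or 0.7; baseline SD 0.5, 0.7 or 1.0; measurement SD 0.3 per result; between-method baseline correlation 1.0 or 0.8; PCR registers all (k = 1) or half (k = 0.5) of the fall. There are 4000 simulated trials per setting, and ranges run over this grid.

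**1. Exact case, no SD needed.** If log10 PCR = a + 0.5 × log10 CFU, then r = 1 and PCR fall = 0.5 × CFU fall. With a CFU fall of 1.4, the PCR fall is 0.70 and the gap is 0.70 log10.

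**2. Behaviour of r with noise.** Pooled over days, n = 45:

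| Baseline correlation | r, full capture | r, half capture | Drop within a setting |
|---|---|---|---|
| 1.0 | 0.87–0.94 | 0.78–0.90 | 0.04–0.09 |
| 0.8 | 0.80–0.82 | 0.69–0.75 | 0.05–0.11 |

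So r does fall, but little relative to its sampling error in small samples. At n = 15 with baseline correlation 1.0 and full capture, the 95% sampling range of Day 14 r is 0.56–0.94 in the widest setting and 0.84–0.98 in the narrowest. Within the same setting, a half-capture trial shows a Day 14 r at least as high as a full-capture trial in 5–38% of replicates at n = 45, 19–45% at n = 15 and 25–46% at n = 10.

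**3. Paired difference against two separate means (Day 14, k = 0.5, gap 0.70).** The SD of the per-patient difference in fall is √[((1 − k) × SD of fall)² + 4 × 0.3²]. This is √(0.04 + 0.36) = 0.63 for SD of fall 0.4, and √(0.1225 + 0.36) = 0.69 for 0.7. The CI half-width is t(0.975, n − 1) × SD/√n. At n = 45 the multiplier is 0.300, giving 0.19–0.21. Simulated averages:

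| Pairs | Half-width, paired | Half-width, unrelated means | CI excludes 0, paired | CI excludes 0, unrelated |
|---|---|---|---|---|
| 45 | 0.19–0.21 | 0.22–0.29 | 100% | 100% |
| 15 | 0.34–0.38 | 0.39–0.52 | 95–98% | 82–96% |
| 10 | 0.44–0.48 | 0.49–0.66 | 80–88% | 57–83% |
| 7 | 0.56–0.62 | 0.61–0.82 | 60–69% | 36–64% |

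At Day 7 the gap is 0.35 and the paired half-width is 0.18–0.19 with 45 pairs and 0.33–0.34 with 15, so Day 7 can only be supportive.

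**4. Different patients in the two means.** If each method's result is missing independently with probability p, the share of contributing patients who enter only one mean is 2p(1 − p)/[(1 − p)² + 2p(1 − p)]. At p = 0.1 this is 0.18/0.99 = 18%; at p = 0.2 it is 0.32/0.96 = 33%. Equal counts of valid observations would not rule this out.

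**5. What pairing does to missing-data bias.** Suppose 20% of CFU results are missing, all in patients with above-average falls, and falls are normal. The mean of either half lies 0.80 SD from the centre, so the mean CFU fall shifts by (0.3 − 0.5)/0.8 × 0.80 SD = −0.20 SD, that is −0.08 to −0.14 log10. With PCR complete, this is the bias in the gap between the two available-case means.

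- Missingness follows the true fall: the paired bias is (1 − k) × (−0.20 SD). This is 0 at full capture and −0.04 to −0.07 at half capture, so half the bias remains.
- Missingness follows the measured fall: the paired bias is −0.20 × [(1 − k) × SD² + 0.18]/√(SD² + 0.18), where 0.18 = 2 × 0.3². This is −0.06 (SD 0.4) and −0.04 (SD 0.7) at full capture, and −0.09 and −0.10 at half capture.
- Missingness completely at random: no such bias for either approach.

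**The case against.** The strongest reply is that the plan already covers most of this. Changes by both methods are tabulated by day and group, the efficacy analysis is repeated on PCR, and SDs, counts and confidence intervals are foreseen. In the illustration above, a gap of 0.70 log10 would be seen at planned enrolment with or without pairing. This stands, and it is why the priority is low. What it leaves open is the uncertainty of the difference itself and whether both means describe the same patients. Both matter more if few pairs remain, and the synopsis states that the study was terminated early.

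Second, the unspecified graphs may include a difference plot, and a scatter plot could reveal a slope of 0.5. This also stands: correlation is the only numerical measure named, not the only tool. A plot alone gives no estimate with an interval.

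Third, if equal falls are not expected, association is a defensible descriptive summary for a secondary method, and no decision hangs on the difference. That is fair for the choice to report a correlation. It does not make a correlation an answer to how consistent the falls are.

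Fourth, the supplied text is at synopsis level, and leaving the type of coefficient open is ordinary there. With the study terminated, new wording may come too late to count as prespecified. Both points limit the claim to what is named and argue for labelling the addition accordingly.

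A reader might also infer that pairing cures the missing-data problem. It does not: step 5 shows residual bias whenever missingness is related to the per-patient difference, and the documents give neither a missingness rate nor a mechanism.

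**Conclusion.** The point holds as a low-priority improvement, not as an error in the efficacy analysis. The named coefficient cannot express how far the PCR fall differs from the CFU fall. The exact example shows this without assumptions: r = 1 with the PCR-based EBA at half the CFU-based EBA. Every other figure rests on assumed SDs, a common linear fall, 50% capture and constructed missingness, and only illustrates size. On those assumptions, pairing adds little at 45 pairs and more at 15 or fewer.

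Two stronger readings are not supported. One is that the plan would overlook a gross disagreement between methods; the side-by-side tables and the parallel PCR analysis would show one in group means. The other is that the trial's efficacy conclusion is in doubt. The primary endpoint, the Kruskal–Wallis dose comparison and the Jonckheere–Terpstra trend test on CFU do not use the correlation, and no rule in the supplied text depends on it.

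**What to change.** Add to the consistency analysis, in substance:

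- For patients with both a CFU and a PCR result at baseline and at the given day, using the average value per measurement point, report the per-patient difference (CFU fall minus PCR fall, log10) as a mean with 95% CI and number of pairs, with a difference plot.
- The main summary is Day 14, pooled over the PBTZ169 groups. Day 7 and by-group results are descriptive, without limits of agreement in small groups. At n = 7 the 95% CI half-width of one limit is 1.66 SD, or 1.05–1.15 log10 for SDs of 0.63–0.69.
- Apply no equivalence margin.
- Label correlation coefficients as by day or pooled, and describe them as association only.
- State that the paired estimate is unbiased only if missingness is unrelated to the per-patient difference.

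Keep the planned graphs, tables and parallel PCR analysis. If the wording is added after data have been seen, label it post hoc.

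Cost: SAP wording and one table or plot from data already collected, with no new samples or visits. Downsides: intervals may be wide if few pairs remain after early termination, the pooled mean averages over doses whose falls may differ, and some bias remains if missingness depends on the fall.
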